7. SAMPLE SIZE JUSTIFICATION

Approximately 32 participants may be enrolled to ensure that at least 28 participants complete the study.

This sample size will provide approximately 80% power to demonstrate a 14-mg/dL difference in the change in PG level from start to the end of the exercise between Lyumjev and Humalog, assuming no true difference in the change in PG level between Lyumjev and Humalog and a SD of 27.9 mg/dL with a 2-sided alpha-level of 0.1. Discontinued participants may be replaced to ensure that 28 participants complete the trial. A replacement participant will be assigned to the same treatment sequence as the participant being replaced.

8. DEFINITION OF ANALYSIS POPULATIONS

The "Safety analysis" population will consist of all participants who are exposed to at least 1 dose of investigational product (IP). Participants will be analyzed according to the intervention they actually received.

The "Full analysis" population will consist of participants who receive at least 1 dose of IP and have completed at least 1 MMTT procedure will be included in the analysis set for the PD analyses. Participants who receive at least 1 dose of insulin during the in-house period and have measurable insulin lispro concentrations will be included in the PK analysis dataset.

The "Modified full analysis" population will consist of all participants who receive both treatments (Lyumjev and Humalog) for at least 1 basal rate reduction (either 50% or 100%) and receive the same dose and meal consumption. Participants who do not keep identical insulin lispro doses for Lyumjev and Humalog or have difference in the consumption of the meal for each visit/period will be excluded from the statistical analysis of the PK and glucodynamic parameters. All participants who receive both treatments with an identical insulin lispro dose for Lyumjev and Humalog will be included for the MMTT PK parameters analysis.

All protocol deviations that occur during the study will be considered for their severity/impact and will be taken into consideration when participants are assigned to analysis populations.

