Upon completion of the exercise period (or once the participant recovers from hypoglycemia [blood glucose reaches **CC**] the pump basal rate will be returned to the participant's usual rate for this time of the day **CC**] and this basal rate will be maintained until the end of MMTT. Participants will be instructed to rest for approximately 30 minutes.

A standardized liquid dinner MMTT containing approximately **CC** of carbohydrate with a fixed nutrient composition **CC** will be administered approximately 1 hour after the exercise assessment (Section 5.3.1.1). The same individualized insulin bolus dose determined from the dose assessment will be used for both arms (Lyumjev or Humalog) for all 4 in-house visits, unless it is required to be changed to protect participant safety (see Section 4.1.2). The insulin bolus dose will be administered immediately prior (0 to 2 minutes) to the meal using a **CC** The meal is to be consumed within 15 minutes.

Participants will be without further oral food intake from the start of each test meal to completion of blood collection 4 hours after the start of the meal (approximately 240 minutes) unless required to treat Level 1 hypoglycemia with symptoms or Level 2 hypoglycemia. Refer to Section 8.2.7.1 and 8.2.7.2 for details. If a participant's plasma glucose concentration rises above for more than hour, **CCl** will be administered. In both situations, blood samples for plasma glucose (for safety and PD) will be taken, and PK samples will be collected as planned during this period per the SoA (Section 1.3). Following completion of study procedures, the study pump will be disconnected and the study CGM system will be removed. The participant's own insulin pump will be re-introduced using a new infusion set, if necessary, for pump compatibility. Participants may leave the CRU at the discretion of the investigator.

Appropriately trained staff must be available until the participants complete the study procedures. The pump can be reused after disinfection, according to the local procedure.

Figure ITSU.3. Study activities during In-house Periods (Visits 3, 4, 5, and 6).

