## 5.3.1.1. Mixed Meal Tolerance Test

On assessment day and on Day 1 of in-house periods, a dinner liquid MMTT will be administered 1 hour after the exercise assessment as mentioned in Sections 4.1.2 and 4.1.3 and as outlined in Section 1.3. The standardized liquid test meal will use **CC** 

The macronutrient composition of the meal will contain approximately 50 g of carbohydrates, approximately CCI of protein, and approximately CCI of fat. Participants will be fasted, except for water, for 4 hours before each test meal and are required to consume the MMTT within approximately CCI approximately CCI and the MMTT meals will be kept consistent across the assessments in the study. Participants will not be allowed to consume water for CCI after dosing apart from fluid provided with the meal. However, water may be consumed freely after post-dose.

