# 6.5. Dose Modification

For the in-house period, there will be no dose modifications of insulin lispro for the MMTT and basal rates unless medically indicated and confirmed between the sponsor clinical pharmacologist/CRP/CRS and the investigator.

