## 9.3.2.2. Glucodynamic Statistical Inference

Statistical analyses comparing PD parameters (described in Section 9.3.2.1) of Lyumjev versus Humalog during exercise with a basal reduction of either 50% or 100% and after the MMTT will be conducted on the modified full analysis set. The exercise and MMTT will be analyzed separately.

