# 9.4. Interim Analysis

No interim analyses are planned for this study. If an unplanned interim analysis is deemed necessary, the Lilly clinical pharmacologist, CRP, investigator, or designee will consult with the appropriate medical director or designee to determine if it is necessary to amend the protocol.

The Lilly clinical pharmacologist/CRP/Lilly study team is unblinded. Data may be accessed and analyzed while the trial is ongoing, but no changes to the study design are planned. The results may help Lilly expedite final delivery and enable planning of future studies. Information that may unblind the study during the analyses will not be reported to the CRU until the study has been unblinded. An assessment committee will not be formed.

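### Read literally, SAP 8's single identical-dose and same-meal rule lets a bolus or test meal given after exercise decide who enters the primary exercise analysis

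*SAP*

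**What the plan says.** **Population.** SAP 8 (and the matching table in Protocol 9.2) builds the modified full analysis set from participants who received both insulins for at least one basal reduction with the same dose and meal. "Participants who do not keep identical insulin lispro doses for Lyumjev and Humalog", or whose meal consumption differs, "will be excluded from the statistical analysis of the PK and glucodynamic parameters". One assessment gets its own rule: participants with an identical lispro dose on both insulins "will be included for the MMTT PK parameters analysis", so the meal condition is waived there and the dose condition stays. Exercise gets no rule of its own.

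**Use.** Protocol 9.3.2.2 states that PD comparisons during exercise and "after the MMTT will be conducted on the modified full analysis set". SAP 9.4.2 calls the exercise glucose change the primary glucodynamic endpoint. It names the modified full analysis set for the secondary endpoints and no set for the primary.

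**Which dose.** Protocol 4.3 requires the dinner MMTT bolus and the basal rates to stay identical across in-house periods. Boluses for the meals before exercise may include corrections (Protocol 4.1.3).

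**Timing and changes.** On in-house Day 1, "a dinner liquid MMTT will be administered 1 hour after the exercise assessment" (Protocol 5.3.1.1). The same bolus is used at all four visits "unless it is required to be changed to protect participant safety" (Protocol 4.1.3). Protocol 6.5 allows no change "unless medically indicated and confirmed between the sponsor clinical pharmacologist/CRP/CRS and the investigator".

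**The concern.** The primary endpoint is complete when exercise ends. The MMTT bolus and the test meal come afterwards and cannot make a recorded start-to-end glucose change less valid. Under SAP 8 as worded, they can still take that change out of the primary analysis.

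This would matter most if the reason for changing the bolus were related to the exercise result, for example a low glucose on leaving the treadmill. The rule would then tend to remove the deepest falls. If Humalog has more of these, its falls are trimmed more and the contrast the trial is designed to detect shrinks. The number analysed also drops below the 28 completers in SAP 7.

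A lesser point is who takes part in the decision. A bolus change is confirmed with sponsor staff, and Protocol 9.4 states: "The Lilly clinical pharmacologist/CRP/Lilly study team is unblinded". Someone who may know the treatment therefore has a part in a decision that affects membership of the primary analysis set.

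**Working it through.** **1. Does the rule reach the primary endpoint?**
- SAP 8: the exclusion covers PK and glucodynamic parameters without restriction.
- SAP 9.4.2: the primary endpoint is labelled glucodynamic, and no other set is named.
- Protocol 9.3.2.2: exercise inference uses the modified full analysis set.
- Protocol 4.3: the MMTT bolus is one of the doses to be kept identical. If every bolus were meant, it would still count.
- Protocol 4.1.3 and 5.3.1.1: that bolus follows exercise by about 1 hour.

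Taken together and literally, an event after the outcome decides entry to the primary analysis.

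**2. The plan's own power figure.** SAP 7 gives n = 28, difference 14 mg/dL, SD 27.9 mg/dL, 2-sided alpha 0.10 and power of about 80%. I take 27.9 as the SD of the within-participant difference. The noncentrality is 14 / (27.9/√28) = 14/5.27 = 2.66 on 27 df, which gives 82.7% by paired t-test. This is in line with the SAP. With fewer participants, power is 80.1% at 26, 78.6% at 25 and 77.0% at 24, so losing three of 28 takes it below 80%.

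**3. Selection model (assumptions, not in the documents).**
- Changes are normal, with within-participant session SD 27.9/√2 = 19.73.
- The correlation ρ between a participant's sessions is 0.3 or 0.5, so the total session SD is 19.73/√(1−ρ) = 23.58 or 27.90.
- The Lyumjev mean is 14 mg/dL above Humalog.
- The cut is the worst fraction f of Humalog sessions. A session in either arm below the cut leads to a bolus change with probability q.
- The Lyumjev-Humalog pair is dropped if either of its sessions is changed.

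Example with ρ = 0.3, f = 5%, q = 1: a Lyumjev session falls below the cut with probability Φ(−1.645 − 14/23.58) = Φ(−2.239) = 1.3%, against 5% for Humalog. About 5 + 1.3 = 6.3% of pairs are affected, or 6.1% after removing the overlap. The imbalance of 5% against 1.3% is what shrinks the contrast.

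Simulation results; ranges cover ρ = 0.3 to 0.5:

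| Share of such sessions changed (q) | Depth (f) | Expected difference, mg/dL | Power |
|---|---|---|---|
| 25% | 5-20% | 13.4-13.8 | 79-82% |
| 50% | 5% | 13.4-13.6 | 80% |
| 50% | 10% | 13.1-13.3 | 78% |
| 50% | 20% | 12.6-13.0 | 74% |
| 100% | 5% | 12.7-13.0 | 77-78% |
| 100% | 10% | 11.9-12.3 | 72-73% |
| 100% | 20% | 10.6-11.3 | 61-64% |

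At q = 100%, pairs lost are about 6%, 12% and 24-25%.

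**4. Variations.**
- Dropping the whole participant instead of the pair at q = 100% gives 11.0-13.1 mg/dL and 54-76% power.
- If the bolus decision follows a variable correlated only 0.5 with the exercise change, q = 50% gives 13.7-13.9 mg/dL and 75-81% power.
- With no true difference and equal handling, the expected difference is 0 and the rejection rate stays at 10.0%.

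All of this is a paired simplification of the SAP mixed model.

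**The case against.** **The wording may intend one condition per assessment.** Protocol 9.3.2.1 and SAP 9.4.1 describe the matching dose, in brackets, as the MMTT bolus or the basal reduction. Those sections cover both MMTT and exercise, and the two are analysed separately. Read that way, the exercise condition is the basal reduction and the problem disappears. This reading is reasonable. However, the bracket stands in sentences about mean summary data, and SAP 8, where the population is defined, does not say it.

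**The primary population is partly inferred.** SAP 9.4.2 is silent, and SAP 3 says the SAP supersedes the protocol's statistical considerations. The statement in SAP 11 that nothing changed is weak evidence, because the primary model in SAP 9.4.2 differs from Protocol 9.3.2.2.1. This stands, and it is a further reason to name the set.

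**The trigger is not documented.** A reader might infer that participants with deep exercise falls will have their bolus cut and so leave the analysis. No section says so. Protocol 4.1.3 and 8.2.7.2 respond to low glucose with oral carbohydrate, stopping exercise, or an earlier meal. The bolus already carries a 25% post-exercise reduction and is tested on the assessment day (Protocol 4.1.2). A real decision would follow glucose near meal time, after any rescue, and stopping exercise at hypoglycemia limits extreme falls. The 100% rows are therefore upper bounds for their depth.

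**Some safeguards exist.** SAP 9.1 highlights excluded participants in listings, and SAP 8 weighs the impact of deviations. The meal in SAP 8 may include lunch, which is a legitimate exercise condition. These help a reader see exclusions but do not change the rule.

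**Conclusion.** The point holds as a defect in the stated rule, with an effect that is probably small and cannot be determined from the documents. SAP 8 read literally lets an MMTT bolus change or an unfinished test meal remove valid exercise data from the primary analysis, and nothing in SAP 8 or SAP 9.4.2 prevents it.

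If 25-50% of the deep sessions led to a change and only the pair were dropped, a true 14 mg/dL would be estimated at about 12.6-13.8 mg/dL with about 74-82% power. Changing the bolus after all of them is an upper bound on the same footing: 10.6-13.0 mg/dL and about 61-78%. These figures rest on the assumed correlation, on bolus changes that track the exercise fall, and on 27.9 being the SD of the paired difference.

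Two stronger readings are not supported. One is that the rule creates false positives: that needs bolus changes handled differently in the two arms, which no section suggests. The other is that unblinded sponsor staff could steer the result: Protocol 6.5 requires a medical indication and the agreement of the investigator, who is blinded (Protocol 6.3). The realistic harm is a modest loss of contrast and power.

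**What to change.** In SAP 8, define an exercise analysis set by conditions up to the end of exercise only:
- both insulins received for at least one basal reduction;
- start- and end-of-exercise glucose available on both;
- the same basal settings and, if wanted, the same pre-exercise lunch.

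Name this set in SAP 9.4.2 for the primary endpoint. Apply the identical MMTT bolus and test-meal conditions to MMTT parameters only. State whether a mismatch removes the pair or the whole participant. The full analysis set is not a ready substitute, because its PD part also requires a completed MMTT.

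Run the set as now written as a sensitivity analysis, and list whom it removes from the exercise comparison and why.

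This is a cheap improvement: a few sentences in the SAP and one extra run of the same model, with no change to conduct, data collection or the primary model. If one condition per assessment was always intended, the edit simply records it.

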9. STATISTICAL METHODOLOGY

9.1 General

Data listings will be provided for all data that is databased. Summary statistics and statistical analysis will only be presented for data where detailed in this SAP. For continuous data, summary statistics will include the arithmetic mean, arithmetic SD, median, min, max and n; for log-normal data (e.g. the PK parameters: AUCs and maximum observed drug concentration [C_{max}]) the geometric mean and geometric CV% will also be presented. For categorical data, frequency count and percentages will be presented. Data listings will be provided for all participants up to the point of withdrawal, with any participants excluded from the relevant population highlighted. Summary statistics and statistical analysis population. For the calculation of summary statistics and statistical analysis, unrounded data will be used.

Mean change from baseline is the mean of all individual participants' change from baseline values. Each individual change from baseline will be calculated by subtracting the individual participant's baseline value from the value at the timepoint. The individual participant's change from baseline values will be used to calculate the mean change from baseline using a SAS procedure such as Proc Univariate.

Data analysis will be performed using SAS[®] Version 9.4 or greater.

9.2 Demographics and Participant Disposition

Participant disposition will be summarized and listed. The demographic variables age, sex, race, ethnicity, duration of diabetes (years), screening glycated hemoglobin (%), screening C-peptide, smoking & alcohol habits, insulin therapy, VO₂ max, body weight, height and body mass index will be summarized and listed. All other demographic variables will be listed only.

9.3 Pharmacokinetic Assessment

9.3.1 Pharmacokinetic Parameter Estimation

The PK analyses will be conducted using standard noncompartmental methods of analysis **CCI** on a computer that meets or exceeds the minimum system requirements for these programs. The version of any software used for the analysis will be documented, and the program will meet the Lilly requirements of software validation. It is possible that other validated equivalent PK software programs may be utilized if appropriate, warranted, and approved by global PK management.

Free serum insulin lispro concentrations will be used to calculate several PK parameters following the meal bolus for the MMTT, including:

• time to early half-maximal drug concentration (early 50% t_{max}),

- time to late half-maximal drug concentration (late 50% t_{max}),
- maximum observed drug concentration (C_{max}),
- time of maximum observed drug concentration (t_{max}),
- AUC from zero to 15 minutes (AUC[0-15min]),
- AUC from time zero to 30 minutes (AUC[0-30min]),
- AUC from time zero to 1 hour (AUC[0-1h]),
- AUC from time zero to 4 hours (AUC[0-4h]),
- AUC from time zero to infinity $(AUC[0-\infty])$.

Other parameters may be calculated as deemed appropriate. Additional partial AUCs may be computed as necessary. If the prebolus insulin lispro concentrations differ between Lyumjev and Humalog prior to the MMTT, the change from baseline values CC

will be used to subtracting the baseline value from all post-dose insulin lispro measurements to calculate the PK parameters. Similarly, the prebolus insulin lispro concentrations differ between Lyumjev and Humalog prior to the lunch before the exercise period, the PK sample collected immediately prior to the bolus will represent as the 0-hour time point for each participant and will be used to subtracting the baseline value from all post-dose insulin lispro measurements to calculate the PK parameters. Other baseline normalization approaches may be explored for assessing the insulin lispro concentrations during the basal reduction. The approach used will be documented in the CSR.

Additionally, an analysis will be conducted to assess the insulin lispro PK during the basal insulin suspension period. PK parameters that were used included the terminal half-life $(t_{1/2})$, time of the last concentration prior to dose (t_{last}) and AUC from time of suspension to the time of the last detectable concentration (AUC[0-t_{last}]). The insulin lispro concentration versus time profile will be compared between Lyumjev and Humalog during this time.

Although attempts will be made to adhere to the scheduled collection times, failure to collect PK samples due to legitimate clinical issues will not be considered as protocol deviations.

Parameters will be individually calculated for each participant based on actual collection times. The mean data will be presented by summary statistics and presented by treatment for those participants who received both treatments (Lyumjev and Humalog) with the same insulin dose (bolus dose for the MMTT or basal reduction) and meal consumption.

PK analysis is the responsibility of Eli Lilly and Company.

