CI		End of exercise assessment Reset pump basal rate to participant's usual rate (maintain individualized single hourly basal rate until the end of MMTT sampling)	Х	Х	Х	Collection of glucose, PK, FFA, and ketones to occur prior to restart of usual basal rate
		Post-exercise resting period				
		Dinner MMTT Administer individualized bolus dose immediately (0-2 minutes) before meal	Xª	X a		CCI
			Xª	X a		
			Xª	Xª		
			Xª	Xª		
		Following collection of PK and glucose samples, remove venous cannula, disconnect study pump, and remove study CGM system Participant resumes usual pump therapy	Xa	Xª		

Approx. hour	Nominal timing	Activity	Insulin (PK)	Plasma glucose	FFA/ Ketones	Other
Discharge from CRU		Participant may leave the CRU at the discretion of the investigator				AEs, product complaints, concomitant medication

Abbreviations: AE = adverse event; CGM = continuous glucose monitoring; CRU = clinical research unit; FFA = free fatty acids; MMTT = mixed meal tolerance test; PK = pharmacokinetics; RPE = rating of perceived exertion; VO2 = oxygen uptake.

a Exact collection timing for PK and glucose samples is provided in footnote of table in Section 1.3.1.

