#### 9.3.3. Pharmacokinetic Analysis

#### 9.3.3.1. Pharmacokinetic Parameter Estimation

Participants who receive at least 1 dose of insulin during the in-house period and have measurable insulin lispro concentrations will be included in the PK analysis dataset.

Pharmacokinetic analyses will be conducted using standard noncompartmental methods of

on a computer

that meets or exceeds the minimum system requirements for these programs. The version of any software used for the analysis will be documented, and the program will meet the Lilly requirements of software validation. It is possible that other validated equivalent PK software programs may be utilized if appropriate, warranted, and approved by global PK management.

Free serum insulin lispro concentrations will be used to calculate several PK parameters following the meal bolus for the MMTT, including time to early half-maximal drug concentration (early 50%  $t_{max}$ ), time to late half-maximal drug concentration (late 50%  $t_{max}$ ), maximum observed drug concentration ( $C_{max}$ ), time of maximum observed drug concentration ( $t_{max}$ ), and area under the plasma concentration time curve (AUC) from zero to 15 minutes (AUC[0-15min]), AUC from time zero to 30 minutes (AUC[0-30min]), AUC from time zero to 1 hour (AUC[0-1h]), AUC from time zero to 4 hours (AUC[0-4h]), and AUC from time zero to infinity (AUC[0- $\infty$ ]). Other parameters may be calculated as deemed appropriate. Additional partial AUCs may be computed as necessary. If the pre-bolus insulin lispro concentrations differ between Lyumjev and Humalog, the average of the two samples collected immediately prior to the correction bolus will represent as the 0-hour time point for each subject and will be used to subtracting the baseline value from all post-dose insulin lispro measurements to calculate the PK parameters.

Additionally, an analysis will be conducted to assess the insulin lispro PK during the basal insulin suspension period. PK parameters that were used included the terminal half-life ( $t_{1/2}$ ), time of the last concentration prior to dose ( $t_{last}$ ) and AUC from time of suspension to the time of the last detectable concentration (AUC[0- $t_{last}$ ]). The insulin lispro concentration versus time profile will be compared between Lyumjev and Humalog during this time.

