4.2 Secondary Objectives and Endpoints

The secondary objectives of the study are:

- To compare the glucodynamic response with Lyumjev versus Humalog during a dinner mixed-meal tolerance test (MMTT) following moderate-intensity aerobic exercise using either 50% or 100% reduction of basal infusion rates, set 60 minutes or 15 minutes before the onset of exercise, respectively
- To compare the PK of insulin lispro between Lyumjev versus Humalog during an MMTT
- To compare the PK of insulin lispro between Lyumjev versus Humalog during 60 minutes of moderate-intensity aerobic exercise using either 50% or 100% reduction of basal infusion rates with Lyumjev or Humalog, set 60 minutes or 15 minutes before the onset of exercise, respectively.

The secondary endpoints of the study are:

- Postprandial PG excursion during the test meal (e.g., area under the plasma concentration versus time curve [AUC] from time 0 to 4 hours [AUC{0-4h}])
- Insulin lispro PK during the MMTT after exercise
- Insulin lispro PK during the exercise.

4.3 **Exploratory Objectives and Endpoints**

The exploratory objectives of the study are:

- To investigate tolerability and safety of Lyumjev and/or Humalog
- To perform an exploratory comparison of glucose variability, time in range, hypoglycemia, and hyperglycemia using continuous glucose monitoring (CGM) profiles obtained from participants receiving Lyumjev and Humalog.

The exploratory endpoints of the study are:

- Incidence of treatment-emergent adverse events (TEAEs), serious adverse events (SAEs), symptomatic hypoglycemia
- Blood ketone levels
- Overall variability (coefficient of variation [CV] and standard deviation [SD])
- Time in range (70 to 180 mg/dL) during exercise, MMTT assessment, overnight period, and for the entire in-house period
- Time in hypoglycemia (<70 and <54 mg/dL) and hyperglycemia (>180 and 140 mg/dL)
- Mean glucose levels.

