9.3.2 Pharmacokinetic Statistical Methodology

The modified full analysis population will be used for these analyses. The PK parameters for the MMTT and during exercise will be analyzed separately.

During the MMTT

Log-transformed PK parameters AUCs, and C_{max} from insulin lispro during the MMTT will be statistically analyzed using a mixed-effect model. The model will include treatment (Lyumjev or

Humalog) and period as fixed effects, and participant as a random effect. The least squares (LS) means will be back-transformed to produce the treatment geometric LS means, ratio of geometric LS means of Lyumjev to Humalog, and corresponding 90% CIs, as well as the p-value, will be reported.

Example of the SAS code is as follows:

```
proc mixed data=xxx;
  class treat period usubjid;
  model logPK = treat period /residual ddfm=kr;
  random usubjid;
  lsmeans treat / cl pdiff alpha=0.1;
  estimate `Lyumjev vs Humalog' treat 1 -1/ CL alpha=0.1;
  ods output lsmeans=lsm diffs=estims;
run;
```

The same analysis without log transformation will be performed on the PK time parameters (early 50% t_{max} , late 50% t_{max} , and t_{max}) during the MMTT. The treatment LS means, treatment difference in LS means between Lyumjev and Humalog, and corresponding 90% CIs, as well as the 2-sided p-value, will be reported. The treatment ratios and 90% CIs for the ratios will be calculated using the Fieller's theorem³, see Appendix 2 for further details on this calculation.

Statistical significance will be achieved when the p-value for a test is less than 0.10.

During exercise

A mixed-effects model without log transformation that includes treatment (Lyumjev with 50% basal reduction, Lyumjev with 100% basal reduction, Humalog with 50% basal reduction, and Humalog with 100% basal reduction), sequence, and period as fixed effects and participant-within-sequence as a random effect may be used for the exploratory PK endpoints during the exercise period. LS means, treatment differences in LS means, and the corresponding 90% CIs for the treatment differences will be estimated from the model. The p-value on the difference between LS means will be used to determine statistical significance. The treatment ratios and 90% CIs for the ratios will be calculated using the Fieller's theorem (Chow and Liu 2009).

Additionally, exploratory analysis may be conducted if deemed necessary upon review of the data.

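### MMTT insulin lispro is baseline-corrected only if pre-bolus levels differ, with no criterion, so the observed data decide whether the secondary PK ratio describes total or bolus exposure

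*SAP*

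**What the plan says.** The SAP (4.2) names as a secondary endpoint "Insulin lispro PK during the MMTT after exercise". For its AUCs and Cmax, SAP 9.3.2 reports the "ratio of geometric LS means of Lyumjev to Humalog, and corresponding 90% CIs", from a model given as "model logPK = treat period /residual ddfm=kr". That model has a two-level treatment term, and no term for the pre-bolus concentration or the basal reduction.

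How the concentrations are prepared depends on a condition. SAP 9.3.1 reads "If the prebolus insulin lispro concentrations differ between Lyumjev and Humalog prior to the MMTT". When the condition is met, the baseline "will be used to subtracting the baseline value from all post-dose insulin lispro measurements to calculate the PK parameters". Protocol 9.3.3.1 opens its sentence in the same way: "If the pre-bolus insulin lispro concentrations differ between Lyumjev and Humalog, the average of the two samples collected immediately prior to the correction bolus" serves as the baseline. Neither document says what happens when the condition is not met; the natural reading is that concentrations are analysed as measured.

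The basal infusion is not off during the meal test. Protocol 1.3.2 tells the site to "maintain individualized single hourly basal rate until the end of MMTT sampling", and Protocol 4.1.3 agrees. The basal rate is restored at the end of exercise, about 1 hour before the MMTT, after a 50% or 100% reduction.

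SAP 9.3.1 assigns the PK analysis to the sponsor. Protocol 4.2 and 9.4 state that the sponsor's clinical pharmacologist and study team are unblinded and may analyse data while the trial is ongoing.

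**The concern.** Basal and bolus are the same molecule, so every MMTT sample contains both. With subtraction, AUC and Cmax approximate bolus exposure. Without it, they describe total exposure. These are different estimands, and observed concentrations choose between them.

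Three features make the choice more than a technicality.

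- *Differ* is undefined. It could mean any numerical difference, a significance test or a clinical threshold. It could be judged per participant, per period, per basal-reduction condition or for the two groups overall.
- The trigger may itself be a treatment effect. Protocol 2.2 expects a faster insulin to show less of a tail after a basal reduction, and the MMTT follows that reduction closely. The definition of one secondary endpoint then depends on a result related to another, lispro PK during exercise.
- The choice is made with treatment known, and nothing downstream compensates. There is no pre-bolus covariate and no commitment to report both versions.

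**Working it through.** **Inputs.** The plan gives no lispro concentration and no planning figure for the PK ratio, so there is no figure of its own to reproduce. The sample size in SAP 7 concerns the glucose endpoint; only its 28 completers are used below. These quantities are assumptions:

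- R: true bolus-only Lyumjev/Humalog ratio
- b: Humalog basal AUC divided by Humalog bolus AUC in the window
- f = b/(1+b): basal share of the Humalog total
- k: Lyumjev/Humalog ratio of basal levels

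**Formula.** Set the Humalog bolus contribution to 1. The Humalog total is 1 + b and the Lyumjev total is R + bk, so

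uncorrected ratio = (R + bk)/(1 + b) = R(1 − f) + kf.

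The corrected ratio is R if basal is constant at its pre-bolus level. A constant basal level shifts Cmax by the same constant, so the formula also holds for Cmax, with f then the basal share of total Cmax. Subtracting a constant does not move tmax.

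**Step 1. Equal basal levels (k = 1).** For example, R = 2.0 and f = 0.3 gives 2.0 × 0.7 + 0.3 = 1.70.

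| Basal share f | R = 1.0 | R = 1.5 | R = 2.0 |
|---|---|---|---|
| 0.09 (b = 0.1) | 1.00 | 1.455 | 1.909 |
| 0.3 | 1.00 | 1.35 | 1.70 |
| 0.5 | 1.00 | 1.25 | 1.50 |
| 0.7 | 1.00 | 1.15 | 1.30 |

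The uncorrected ratio lies between 1 and R when R is not 1. When R = 1, nothing changes.

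**Step 2. Unequal basal levels, correction skipped (b = 0.5).**

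- R = 1.5, k = 0.8: (1.5 + 0.4)/1.5 = 1.267
- R = 1.0, k = 1.25: (1.0 + 0.625)/1.5 = 1.083, away from 1
- R = 1.5, k = 1.67: (1.5 + 0.835)/1.5 = 1.557, above R

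The pull is towards k.

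**Step 3. The switch in operation.** A simulation took R = 1.5, b = 0.5, a within-participant CV of 30%, 28 participants with one Lyumjev/Humalog pair each, and 20,000 runs. *Differ* was read as p < 0.10 on the baselines. Subtraction was taken as exact.

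| True k | Correction triggered | Corrected ratio | Uncorrected ratio | Average ratio reported |
|---|---|---|---|---|
| 1.0 | 10% | 1.50 | 1.32 | 1.34 |
| 0.9 | 37% | 1.50 | 1.29 | 1.38 |
| 0.8 | 87% | 1.50 | 1.25 | 1.47 |

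The bolus ratio is the same in every row; the reported average moves with the baselines.

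**Step 4. Does subtraction recover R?** Only if the pre-bolus level equals the basal level during the meal test. If it is half of the later level, a residual 0.5b stays in. With R = 1.5 and b = 0.5 the corrected ratio is (1.5 + 0.25)/(1 + 0.25) = 1.40. The uncorrected ratio is (1.5 + 0.5)/1.5 = 1.333, so subtraction recovers (1.40 − 1.333)/(1.50 − 1.333) = 40% of the gap.

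**The case against.** The objective speaks of lispro PK during an MMTT, not of bolus exposure. At identical basal rates and bolus doses, a total-exposure ratio is a legitimate target. This stands: total exposure is not wrong in itself. The defect is that neither version is fixed as the analysis.

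Read literally, measured concentrations almost always differ, so correction would nearly always apply and switching would be rare. That is possible, but nothing in either document makes it the intended reading.

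The SAP sentence is partly redacted, so a criterion might be hidden. The redaction falls after the if-clause, where the baseline definition sits. The readable protocol sentence gives that definition and no criterion. The SAP's remark that the approach will be documented in the CSR follows a sentence on other normalisation approaches for the basal-reduction period, and disclosure afterwards is not prespecification.

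The consequence is limited: the primary glucose endpoint and the sample size are untouched, and SAP 9.1 lists all databased data, so the other version can be recomputed. This stands and caps the importance of the point.

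A reader might infer that the ratio is diluted whenever correction is skipped. The documents do not support that. Steps 1 and 2 show no dilution when R = 1 and k = 1, and bias away from 1 or inflation for some k. With the same bolus in both arms, R may be near 1 for AUC(0-4h) and AUC(0-∞). Dilution is more plausible for the early partial AUCs.

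**Conclusion.** The point holds as a defective rule. An undefined, data-dependent condition, applied with treatment known, decides whether a named secondary ratio describes total or approximately bolus exposure. This rests on the wording of both documents and needs no assumed numbers.

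Dilution towards 1 follows for AUCs and Cmax only when basal levels are similar, the basal share is not negligible and the true bolus ratio is not 1. Its size is illustrative because R and f are both assumed: a true 2.0 would read between about 1.9 and 1.3 over basal shares of 0.09 to 0.7. If basal levels differ, the uncorrected ratio moves towards the basal ratio.

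A reader might also infer that the sponsor would use the switch to favour a product. The documents show that the freedom exists, not that it would be used that way.

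**What to change.** In SAP 9.3.1, delete the condition. Name one version as the secondary MMTT PK analysis for every participant and period, preferably the pre-bolus-subtracted one, and always report the other as a sensitivity analysis. The similarly worded trigger before lunch, in the same section, needs the same edit, and Protocol 9.3.3.1 should be aligned.

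Two additions are needed for subtraction to work as a fixed rule.

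- A rule for zero or negative corrected AUCs. SAP 9.3.2 log-transforms AUCs with no fallback, and an early interval such as AUC(0-15min) could be non-positive after subtraction. The untransformed analysis that SAP 9.4.2 already provides for glucodynamic parameters could serve.
- A statement that subtraction may under-correct, because basal is restored only about 1 hour before the MMTT and the pre-bolus level may lie below the later basal level.

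The cost is SAP wording and one extra table, with no new data. Corrected values will be slightly noisier.
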